The Safety and Efficacy of the Transnasal Humidified Rapid-Insufflation Ventilatory Exchange (THRIVE) for Short Laryngologic Surgical Procedures

Statistical Analysis Plan

NCT03091179

June 20, 2019

Means and standard deviations were calculated for each of the patient characteristics. The statistical significance of differences between THRIVE and non-THRIVE patients was assessed using a *t*-test for all patient characteristics except gender, where a chi-square test was used. No adjustments were made to the statistical significance threshold for multiple comparisons, and our results should be viewed as exploratory.

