STUDY PROTOCOL: THRIVE AND LARYNGOLOGIC SURGERY

1

**The Safety and Efficacy of the Transnasal Humidified Rapid-Insufflation Ventilatory Exchange (THRIVE)
for Short Laryngologic Surgical Procedures**

Study Protocol

NCT03091179

February 15, 2017

STUDY PROTOCOL: THRIVE AND LARYNGOLOGIC SURGERY

STUDY OBJECTIVES

1. DETERMINING THE SAFETY AND EFFICACY OF THRIVE FOR SHORT LARYNGOLOGIC SURGERY.

THRIVE should improve operating conditions, decrease surgical time, and potentially lead to better patient outcomes. The safety of THRIVE for short laryngologic surgery has not been formally investigated, and will be explored in this study. With the patient anesthetized, apneic, and adequately oxygenated with THRIVE, the build up of carbon dioxide in patient's blood (PaCO_2) and ensuing acute hypercapnic acidosis will be the main factors limiting the duration of THRIVE administration. At present, the rate of PaCO_2 rise with THRIVE has not been directly investigated, but is suggested to be between 1.1 and 1.8 mm Hg per minute. It is expected that the short duration of laryngologic procedures explored in this study (not exceeding 30 min) will not lead to substantial rise of PaCO_2 . The PaCO_2 rise to 75 mm Hg is considered a safe level for moderate hypercapnia in patients without significant comorbidities (see Exclusion Criteria).

2. DETERMINING POSSIBLE BENEFICIAL EFFECT OF THRIVE ON IMMEDIATE POSTOPERATIVE RECOVERY in PACU, QUALITY OF POSTOPERATIVE RECOVERY (QoR15), OPIOD CONSUMTION, AND VOICE HANDICAP INDEX (VHI-10).

EXCLUSION CRITERIA

1. Patients with significantly decreased myocardial function (ejection fraction < 50%)
2. Patients with abnormal cardiac rhythm and conduction abnormalities, except for patients with isolated, asymptomatic premature atrial and ventricular contractions.
3. Patients with significant peripheral vascular disease, such as those with the symptoms of intermittent claudication.
4. Patients with known significant cerebrovascular disease, such as history of cerebrovascular accidents (CVAs) and transient ischemic attacks (TIAs).
5. Patients with significant renal insufficiency, as manifested by estimated glomerular filtration rate (eGFR) < 60 ml/min/1.73 m².
6. Patients with electrolyte (K+, Ca++) abnormalities, as determined by the lab values outside of a normal range.

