xiv. Functional home recovery profile after surgery during first postop week

- Pain scores
- PO opioid requirements
- PO non-opioid (Tylenol) requirements
- QoR15
- Return to daily activities
- Return to work

xv. VHI-10 (Voice Handicap Index)

- Preop vs 1 month after surgery

STUDY PROTOCOL: THRIVE AND LARYNGOLOGIC SURGERY

OPERATING ROOM PREPARATION

1. All drugs, airway supplies, eye tape, per routine.
2. 5.0 MLT ETT.
3. Precut large Tegaderm for securing ETT to the chin in left corner of mouth.
4. Video laryngoscopy system: either a Glidescope or Storz CMAC system.
5. Monsoon JV with connection tubing for suspension laryngoscope, and full humidification set up.
6. Four channel Alaris pump with:
 - a. NS carrier at 50 ml/hr
 - b. Propofol drip
 - c. Remifentanil drip
 - d. Check to assure tight connections throughout
7. 20 ml NS syringe in-line for chasing the induction and IVP drugs intraop. **Please minimize IVF beyond 10 ml/kg total (5 ml/kg prior to induction, and 5 ml/kg as required intraoperatively), due to high incidence of urinary retention in male patients.**
8. Working PNS with pads (make sure the battery is fresh).
9. Sedline monitor.

STUDY PROTOCOL: THRIVE AND LARYNGOLOGIC SURGERY

	THRIVE GROUP	CONTROL GROUP
PREOP and PREMEDICATION	
 • Obtain patient's consent. Make 2 copies: one for the chart, and another for the patient. • Randomize the patient to either THRIVE or CONTROL group (5.0 MLT or supraglottic jet). Note: patient is blinded to the modality used. • Obtain preop VAS pain score, QoR15 and VHI. • Patient's folder contains: a copy of consent, postop diaries, QoR15, VHI, all stamped with patient's stickers, and 3 return, pre-stamped envelopes. Enter DOS and subject # in diaries, QoR15, VHI. • Study folder contains: consent, preop QoR15, VHI, intraop and PACU data collection sheets, all stamped with patient's stickers. Place patient's sticker on study folder. • Peripheral IV, 20 g R upper extremity (preferred), tape securely straight out. • Midazolam 0.007 mg/kg incremental doses to achieve sufficient anxiolysis, not to exceed 0.025 mg/kg total dose, unless severe anxiety. For elderly patients (70-80 y.o), limit total dose of Midazolam to 0.5 mg. 	

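### The SAP names no baseline adjustment for VHI-10 or QoR15, although preop scores are collected in both arms; ANCOVA offers a cheap precision gain of unknown size

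*SAP*

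**What the plan says.** The SAP is a single paragraph. It describes means and standard deviations for patient characteristics and a t-test between THRIVE and non-THRIVE patients "for all patient characteristics except gender, where a chi-square test was used". No covariate, change score, follow-up time or regression model is named. No multiplicity adjustment is made, and the SAP adds that "our results should be viewed as exploratory".

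Objective 2 of the protocol names "QUALITY OF POSTOPERATIVE RECOVERY (QoR15), OPIOD CONSUMTION, AND VOICE HANDICAP INDEX (VHI-10") among the outcomes on which THRIVE may have a beneficial effect. The end-point list places both under the heading for both groups:

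- VHI-10 (item xv) is given as "Preop vs 1 month after surgery".
- QoR15 (item xiv) falls under "Functional home recovery profile after surgery during first postop week", with no particular day stated.

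The preop and premedication row of the management table, whose text serves both arms, instructs staff: "Obtain preop VAS pain score, QoR15 and VHI". The same row lists "Randomize the patient to either THRIVE or CONTROL group" ahead of the preop scores, followed by "Note: patient is blinded to the modality used".

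**The concern.** When an outcome score is also measured before treatment in a randomised trial, adjusting for the preop score removes the part of the between-patient variation that it predicts. An unadjusted t-test leaves that variation in the standard error. The baseline scores here are already planned and collected, so leaving them out saves nothing.

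The SAP presents its results as exploratory, so the estimates and their intervals carry the message more than the p-values do. If the preop scores are moderately predictive, the intervals for two outcomes named in objective 2 would be wider than the collected data allow.

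**Working it through.** **Inputs.** The documents state no sample size, SD, effect size, correlation or numeric significance level, so there is no figure of the plan to reproduce. Everything below is assumed: 1:1 allocation, a linear relation with common slope, rho from 0 to 0.7, and total N of 100, 40 or 20.

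**Large-sample variance of the group difference,** relative to a t-test on the follow-up score (= 1), with equal SDs at both times:

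- change-score t-test: 2(1 − rho)
- ANCOVA: 1 − rho²

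| rho | Follow-up | Change | ANCOVA | ANCOVA vs follow-up | ANCOVA vs change |
|---|---|---|---|---|---|
| 0.3 | 1 | 1.40 | 0.91 | −9% | −35% |
| 0.5 | 1 | 1.00 | 0.75 | −25% | −25% |
| 0.7 | 1 | 0.60 | 0.51 | −49% | −15% |

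**Finite-sample cost.** Estimating the slope multiplies the ANCOVA variance by 1 + 1/(N − 4):

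- N = 100: 1 + 1/96 = 1.010
- N = 40: 1 + 1/36 = 1.028
- N = 20: 1 + 1/16 = 1.063

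Thus at rho 0 the cost is about 1% in variance with 50 per arm and 3% with 20 per arm.

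**Break-even against the follow-up t-test.** Setting (1 − rho²)(1 + 1/(N − 4)) = 1 gives rho = sqrt(1 − 1/(1 + 1/(N − 4))). This is 0.10 at N = 100, 0.16 at N = 40 and 0.24 at N = 20.

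**Change in 95% CI width with ANCOVA,** from the square root of the variance ratio times the ratio of t quantiles (N − 3 against N − 2 degrees of freedom):

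| rho | vs follow-up, 50 per arm | vs follow-up, 20 per arm | vs change, 50 per arm |
|---|---|---|---|
| 0 | +0.5% | +1.5% | −29% |
| 0.1 | 0% | +1% | −25% |
| 0.2 | −1.5% | −0.6% | −22% |
| 0.3 | −4% | −3% | −19% |
| 0.5 | −13% | −12% | −13% |
| 0.7 | −28% | −27% | −7% |

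**Unequal SDs.** With k = preop SD / follow-up SD, the change-score variance is 1 + k² − 2·rho·k. At rho 0.5 and k = 0.75, 1 and 1.5 this is 0.8125, 1.00 and 1.75. Against 0.75 for ANCOVA, the saving is 8%, 25% and 57%. At rho 0.7 and k = 0.75 it is 0.5125 against 0.51, so almost nothing is saved. There the regression slope, 0.7/0.75 = 0.93, is close to 1, which is the case in which a change score does nearly as well.

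**Why returned QoR15 values should not simply be averaged.** Assume seven daily scores rising by 20 points in equal steps and no treatment effect. In one arm values are missing evenly across days. In the other, 26% are missing on average, falling linearly from 52% on day 1 to 0% on day 7. Counting the score from 0 on day 1, the evenly missing arm averages 10. In the other arm the returned fractions (0.48 up to 1.00) sum to 5.18 and the returned scores to 59.9, giving 59.9/5.18 = 11.6. The spurious difference is about 1.6 points; with the same pattern in both arms there is none.

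**The case against.** The strongest reply is that this is a preference for efficiency resting on unseen inputs. The t-test is valid. Nothing in the documents shows that rho exceeds the break-even value: surgery lies between the two VHI-10 measurements, and QoR15 is taken during early recovery, so preop scores may predict either outcome only weakly. At rho 0.3 the interval narrows by just 3% to 4% against a follow-up t-test. The larger savings against a change score matter only if change scores are analysed. The SAP never says so, and the VHI-10 end-point label merely permits that reading. The SAP also calls its results exploratory, and it is dated June 2019 and written in the past tense, so a new model would probably be post hoc. All of this stands, and it limits how strongly the change can be urged. It does not remove the point, because the worst-case cost is small.

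A reader might go further and infer that VHI-10 and QoR15 have been left without any analysis. The text does not support singling them out. The SAP speaks of patient characteristics and names no outcome at all, so on a literal reading the silence is general and covers objective 1 as well. Whether the t-test was meant to extend to outcomes cannot be settled from the documents. The precision argument applies only if it was.

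**Conclusion.** The point holds as a modest one. Baseline scores are collected in both arms for two objective 2 outcomes, and the SAP names no adjustment for them. If the unadjusted t-test is used, ANCOVA would generally give tighter intervals. Over rho 0 to 0.7, the change in CI width against a follow-up t-test runs from 1.5% wider (20 per arm, rho 0) to 28% narrower (50 per arm, rho 0.7). Where in that range the trial lies is unknown, because rho, the SDs and N are all assumed.

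A reader might infer that the unadjusted comparison is biased. It is not: with randomised groups, the follow-up and change-score t-tests are both valid, and what is at issue is efficiency alone. Nor do the documents support calling the loss material. The change is therefore one to consider; no result has to be withheld for want of it.

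**What to change.** 1. **VHI-10.** Analyse the 1-month score by ANCOVA on randomised group with the preop VHI-10 score as covariate. Report the adjusted difference with its 95% CI. There is one follow-up time, so no choice of day arises.
2. **QoR15.** Analyse the first-week score with the preop QoR15 score as covariate. If it was recorded more than once, use a repeated-measures model with day as a factor, or a single day fixed before results were seen. Do not average whichever values came back.
3. **Reporting.** Give the number of forms analysed per arm for each outcome.
4. **Timing of the preop scores.** Confirm that they were taken before treatment. The protocol lists randomisation first; patient blinding limits the concern but does not replace the check.
5. **Status.** If results have been seen, label the adjusted analysis post hoc and show the unadjusted difference beside it.

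The cost is a few sentences in the SAP and a few lines of code. For ANCOVA it is also one degree of freedom. No patients or measurements are added.
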